### 7.3.2. Evaluation of Causality

The relationship of AEs to study drug is a clinical decision that will be made, based on all available information, by the investigator, who will answer the following question:

Is there a reasonable possibility that the AE was caused by the study drug?

The possible answers are:

**Not Related:** There is no reasonable possibility that the event may have been caused by the study drug

**Related:** There is a reasonable possibility that the event may have been caused by the study drug (ie, a causal relationship cannot reasonably be ruled out)

The investigator will provide a comment on the SAE reporting form to explain the basis of the causality assessment for SAEs.

#### 7.3.2.1 Causality Evaluation Factors

Factors to consider when determining the relationship of an AE to study drug are included below.

**Not Related:**

- Existence of a clear alternative explanation or nonplausibility (eg, the patient is struck by an automobile when there is no indication that the drug caused disorientation, or cancer diagnosed a few days after first drug administration)
- Due to external causes such as other treatment/s being administered
- Due to the patient's disease state or clinical condition
- Does not follow a reasonable temporal sequence following the time of administration of the dose of study drug
- Does not reappear or worsen when dosing with study drug is resumed (ie, negative re-challenge)
- Is not a known response to the study drug based upon preclinical data or prior clinical data

**Related:**

- Could not be explained by other treatment/s being administered
- Could not be explained by the patient's disease state or clinical condition
- Follows a reasonable temporal sequence following the time of administration of the dose of study drug
- Resolves or improves after discontinuation of study drug
- Reappears or worsens when dosing with study drug is resumed (ie, positive re-challenge)
- Known to be a response to the study drug based upon preclinical data or prior clinical data
- Known to be strongly associated with drug exposure (eg, angioedema, Stevens-Johnson Syndrome)

#### **7.4. Safety Monitoring**

The investigator will monitor the safety of study patients at his/her site(s) as per the requirements of this protocol and consistent with current Good Clinical Practice (GCP). Any questions or concerns should be discussed with the sponsor in a timely fashion. The sponsor will monitor the safety data from across all study sites. The medical monitor will have primary responsibility for the emerging safety profile of the compound. The study monitor will be supported by other departments (eg, Pharmacovigilance and Risk Management; Biostatistics and Data Management). Safety monitoring will be performed on an on-going basis (eg, individual review of SAEs) and on a periodic cumulative aggregate basis.

#### **7.5. Investigator Alert Notification**

Regeneron (or designee) will inform all investigators participating in this clinical trial, as well as in any other clinical trial using the same investigational drug, of any SAE that meets the relevant requirements for expedited reporting (an AE that is serious, unexpected based on the Investigator's Brochure, and has a reasonable suspected causal relationship to the medicinal/investigational product).

## 8. STUDY VARIABLES

### 8.1. Demographic and Baseline Characteristics

Baseline characteristics will include standard demography (eg, age, race, weight, height), disease characteristics including medical history, and medication history for each patient.

### 8.2. Primary and Secondary Endpoints

#### 8.2.1. Primary Endpoint

- The primary endpoint in the study is the incidence and rate (events per patient-year) of treatment-emergent adverse events (TEAEs) through the last study visit.

#### 8.2.2. Secondary Endpoints

The secondary endpoints are:

- Key secondary endpoints
  - Incidence and rate (events per patient-year) of SAEs and AESIs
  - Proportion of patients with IGA = 0-1 at each visit
  - Proportion of patients with EASI-75 ( $\geq 75\%$  reduction in EASI scores from baseline of the parent study) at each visit
- Other secondary endpoints:
  - Proportion of patients with low disease activity state (eg, IGA  $\leq 2$ ) at each visit
  - Change and percent change from baseline in EASI score at each visit
  - Proportion of patients with EASI-50 ( $\geq 50\%$  reduction in EASI scores from baseline of the parent study) at each visit
  - Proportion of patients with EASI-90 ( $\geq 90\%$  reduction in EASI scores from baseline of the parent study) at each visit
  - Change and percent change from baseline in Pruritus NRS
  - Proportion of patients with improvement (reduction) of Pruritus NRS  $\geq 3$  from baseline
  - Proportion of patients with improvement (reduction) of Pruritus NRS  $\geq 4$  from baseline
  - Proportion of patients requiring rescue treatment:
    - Overall
    - Systemic treatment
      - Systemic corticosteroids
      - Systemic immunosuppressive drugs

- Phototherapy
- Number of days on topical medication (per patient-year)
- Proportion of patients using topical medications over various periods during the study
- Changes from baseline to prespecified time points through the end of the study:
  - DLQI
  - POEM
  - EQ-5D

### 8.2.3. Sub-Study Endpoints

#### Primary Endpoints

- Incidence of AESIs through the last study visit after switching to the new dupilumab drug product.

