**Figure 3: Relationship Between Visit Schedules in Main OLE Study and Sub-Study**

Abbreviations: D=day; EOS=end of study; EOT=end of treatment; SOE=schedule of events; V=visit; W=week.

Patients will enter the sub-study at various time points during participation in the main OLE study (V41, V43, or V44). At V41, V43, or V44 (which will vary from patient to patient but should be a scheduled in-clinic visit), patients who are willing to participate in the sub-study and who are eligible, will enter V1a of the sub-study. At V1a, patients should have assessments and procedures performed as per both the SOE of the OLE study (V41, V43, or V44) as well as the sub-study (V1a) (any redundant procedures will only be performed once). This optional sub-study requires a separate consent. Patients who do not enter the sub-study will continue to follow the SOE for the main study.

The first new dupilumab drug product administration should occur 14 days ( $\pm 3$  days; preferably  $\pm 1$  day) after the previous administration of the current dupilumab drug product in the main study.

For patients who began treatment with the new dupilumab drug product at V43 or V44 of the main study, the last dose of the new dupilumab drug product will be administered at sub-study V3a.

V4a only applies to patients who switched to the new dupilumab drug product at V41 of the main study. The last dose for these patients will be administered at sub-study V4a.

The EOS visit occurs 12 weeks after the last dose of dupilumab in either the main OLE study or the sub-study. The same EOS assessments are performed for patients receiving the current dupilumab drug product or the new dupilumab drug product.

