### 3.3. Planned Interim Analysis

No interim analysis is planned for this open-label study. Summaries of the data may be provided for regulatory agency interactions and for other clinical program purposes.

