**6.2.6.3. Sub-Study Visit 3a/Day 85a/Week 12a ( $\pm 3$  days)**

This visit should occur on sub-study day 85a ( $\pm 3$  days). Although the protocol allows a visit window of  $\pm 3$  days, it is strongly recommended that visit 3a occurs 14 days ( $\pm 1$  day) after the self-injection of the new dupilumab drug product on sub-study day 71a.

The following information will be collected:

- AEs
- Concomitant medications/procedures;

The following procedures and assessments will be conducted:

- Vital signs (heart rate, blood pressure, body temperature, and respiration rate)
- Ophthalmology exam (select sites and patients)
- IGA
- EASI
- Laboratory samples:
  - Hematology w/differential
  - Serum chemistry
  - Urine pregnancy test – for women of childbearing potential
  - Drug concentration sample
  - ADA sample

- Patient assessment of pruritus intensity via IVRS/IWRS (weekly)
- If needed, counsel patient on proper dosing diary completion/reporting of each dose of study drug that is administered outside of the clinic
- Study drug accountability
- Administer study drug (new dupilumab drug product)
- Study drug dispensation (Note: patients who switched at visit 41 only)

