#### **6.2.6.4. Sub-Study Visit 4a/Day 169a/Week 24a ( $\pm 3$ days)**

Note: This visit is only applicable to patients who switched to the new dupilumab drug product at visit 41 of the main study.

The following information will be collected:

- AEs
- Concomitant medications/procedures;

The following procedures and assessments will be conducted:

- Vital signs (heart rate, blood pressure, body temperature, and respiration rate)
- Ophthalmology exam (select sites and patients)
- IGA
- EASI
- Laboratory samples:
  - Urine pregnancy test – for women of childbearing potential
  - Drug concentration sample
  - ADA sample
- Patient assessment of pruritus intensity via IVRS/IWRS (weekly)
- If needed, counsel patient on proper dosing diary completion/reporting of each dose of study drug that is administered outside of the clinic
- Study drug accountability
- Administer study drug (new dupilumab drug product)

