#### 9.5.6. Analysis of the Sub-Study

Demographic and baseline characteristics will be summarized descriptively. Safety analyses will be conducted in descriptive fashion as described in Section 9.5.2.1 and Section 9.5.2.2. Efficacy analyses will be conducted in descriptive fashion as described in Section 9.5.3. Treatment compliance and treatment exposure will be analyzed in a similar fashion as described in Section 9.5.2.3 and Section 9.5.2.4.

Under Amendment 10, a primary analysis of the sub-study is planned once all patients who enter the sub-study complete 12 weeks of the new dupilumab drug product treatment period (sub-study week 12a visit or earlier for those patients who are withdrawn prematurely from the study).

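### The sub-study's primary endpoint runs to the last study visit (week 24a or 36a), but its primary analysis is triggered at week 12a, with no common cut and no stated final analysis

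*Protocol*

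**What the plan says.** The Synopsis and Protocol Section 8.2.3 give the sub-study one primary endpoint: "Incidence of AESIs through the last study visit after switching to the new dupilumab drug product".

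Section 9.5.6 says that "a primary analysis of the sub-study is planned once all patients who enter the sub-study complete 12 weeks" of new-product treatment. It clarifies the milestone as "sub-study week 12a visit or earlier for those patients who are withdrawn prematurely from the study".

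The last study visit depends on the point of entry. Under Figure 3, for patients entering at main-study visit 43 or 44, "the last dose of the new dupilumab drug product will be administered at sub-study V3a". For those entering at visit 41, "The last dose for these patients will be administered at sub-study V4a". The notes to Figures 2 and 3 put the end-of-study visit 12 weeks after the last dose. Section 7.2.6 collects adverse events to the last study visit. Section 9.5.2.1, which Section 9.5.6 applies to the sub-study, runs the treatment-emergent period to end of study.

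Section 9.5.6.4 plans AESI counts and percentages, and also exposure-adjusted AESIs. Section 3.3 states that "No interim analysis is planned for this open-label study", then allows data summaries for regulatory and program purposes. SAP version 2.0 rests on protocol amendments 6 to 8 (SAP Section 1.2.4). The sub-study came in with amendment 10, so that SAP does not cover it.

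**The concern.** An analysis called primary would normally be expected to report the primary endpoint. Here the endpoint's observation window is still open for some or all patients when the analysis is triggered. The protocol does not say which AESI data enter that analysis: events up to a fixed sub-study day, or everything collected by the calendar cut. It also names no later sub-study analysis that would close the window.

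The sub-study exists to give clinical evidence of safe use after the switch (Section 1.2.3), in about 50 patients. A headline AESI percentage carrying the Section 8.2.3 label would be inaccurate for anyone still in treatment or follow-up. Injection site reactions that are serious, severe or last more than 24 hours are AESIs added for this sub-study alone (Section 7.2.3). The main study's AESI tables would therefore not automatically supply what is missing.

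**Working it through.** **Inputs.** Entry visits 41, 43 and 44 are main-study weeks 236, 252 and 260 (Tables 6 and 7). The last new-product dose is at "Sub-Study Visit 3a/Day 85a/Week 12a" for visit 43/44 entrants and at "Sub-Study Visit 4a/Day 169a/Week 24a" for visit 41 entrants. The end-of-study visit is the last-dose week plus 12.

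**Reproducing the protocol's own figure.** Section 3.1 says entry at visit 43 or 44 lengthens treatment by 4 or 12 weeks. Extension = entry week + weeks on new product − 260:

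- Visit 41: 236 + 24 − 260 = 0
- Visit 43: 252 + 12 − 260 = 4
- Visit 44: 260 + 12 − 260 = 12

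This matches, so the timeline is read as intended.

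**Endpoint window against trigger.**

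| Entry | Last dose | End of study | Observed at week 12a | Still to come |
|---|---|---|---|---|
| Visit 43/44 | week 12a | 12 + 12 = week 24a (day 169a) | 12/24 = 50% | 12 weeks, off drug |
| Visit 41 | week 24a | 24 + 12 = week 36a (day 253a) | 12/36 = 33% | 24 weeks: 12 on drug, 12 off |

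These shares describe a patient who is exactly at week 12a at the cut, that is, the last entrant.

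**Doses not followed, for that last entrant.** Dosing every 2 weeks gives 7 doses from week 0a to 12a; the one given at the week-12a visit has no follow-up. For a visit 41 entrant there are 13 doses from week 0a to 24a; the 7 from week 12a to 24a are not covered.

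**All patients, not only the last.** The documents do not give the entry span. As an assumption, let entry be uniform over A weeks in each group, with the cut at A + 12 and no early withdrawal. The share past end of study is then (A − 12)/A for visit 43/44 entrants and (A − 24)/A for visit 41 entrants, or zero if negative.

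| A (weeks) | Visit 43/44 | Visit 41 |
|---|---|---|
| 12 or less | 0% | 0% |
| 16 | 4/16 = 25% | 0% |
| 24 | 12/24 = 50% | 0% |
| 36 | 24/36 = 67% | 12/36 = 33% |
| 52 | 40/52 = 77% | 28/52 = 54% |

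Without a common cut, follow-up among patients still in the study runs from 12 weeks up to 24 or 36 weeks, according to entry date and entry visit. Patients who withdraw count towards the trigger on withdrawal, although Section 6.2.8 also asks them back 12 weeks after their last dose.

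**Direction.** The proportion of patients with at least one AESI cannot fall as follow-up lengthens. A truncated window can only equal or understate the through-last-visit figure.

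**The case against.** Section 9.5.6 plans a primary analysis; it does not call it the only or the final one, and does not say in words that it closes the primary endpoint. The methods in Section 9.5.6.4 are not tied to week 12a, Table 8 keeps sampling at week 24a and end of study, and adverse events are collected throughout. A first cut at week 12a, completed at study end, is a fair reading. Section 3.3 foresees early summaries. Exposure-adjusted AESIs are prespecified. Section 9 leaves detail to a SAP covering the sub-study, and this study's SAP is where cut-off rules have been placed (SAP Sections 10.7 and 10.8).

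Much of this stands. A reader might infer that the plan cannot deliver its primary endpoint, or that week 12a is the only look. The documents do not say so: the data will be collected, and nothing forbids a later report. What remains is that the protocol neither limits the primary endpoint to week 12a nor names the analysis that would report it in full. The contrast is with the exploratory IGA endpoint, which Section 8.2.3 ties expressly to week 12a. Exposure adjustment addresses unequal follow-up, but it gives a rate, not the stated incidence, and cannot supply weeks not yet observed. A later SAP could repair this, but the mismatch of endpoint and trigger is in the protocol.

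**Conclusion.** The concern holds as a mismatch between endpoint, data cut and timing. At the week-12a trigger the primary endpoint is incomplete for every patient who has not reached end of study: half the window is seen for the last visit 43/44 entrant and a third for the last visit 41 entrant. How many patients are affected depends on the entry span, which is not given.

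The sub-study has no hypothesis and no power calculation (Sections 9.5.6.1 and 9.5.6.2), so no error rate or decision rule is at stake. The result at risk is a descriptive safety figure that is truncated, mixed in follow-up and open to mislabelling.

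Two stronger inferences are not supported. One is a numerical shortfall: it would need an AESI risk that the documents do not give, held constant through off-drug weeks, whereas injection site reactions follow injections. The other is that 50% or 33% applies to all of the roughly 50 patients; those shares belong to the last entrants, and earlier ones may have finished.

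**What to change.** In Section 9.5.6, and in the SAP that covers the sub-study:

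1. State that the week-12a analysis reports AESIs up to a common sub-study cut, through week 12a, for every patient. Label it so, and show it with the exposure-adjusted rate.
2. Add a final sub-study analysis after the last patient's end-of-study visit, reporting the primary endpoint through the last study visit as Section 8.2.3 defines it.

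The final analysis then counts events after the week-12a dose, the visit 41 entrants' second 12 weeks on the new product, and the off-drug follow-up. Shortening the primary endpoint itself to week 12a would also align the text, but would remove all three from the primary safety measure.

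The cost is protocol and SAP wording and one re-run of the same tables, with no extra visits or patients. The full primary endpoint would be available later than the week-12a trigger: by 12 weeks if the last patient entered at visit 43 or 44, and by up to 24 weeks if at visit 41.

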#### Secondary Endpoints

- Trough concentrations ( $C_{\text{trough}}$ ) of functional dupilumab in serum before and after switching to the new dupilumab drug product
- Incidence of treatment-emergent ADA response in patients receiving the new dupilumab drug product

#### Exploratory Endpoints

- Proportion of patients with IGA = 0 or 1 before (at sub-study week 0a [sub-study baseline]) and after switching to new dupilumab drug product (at sub-study week 12a)
- Change and percent change from baseline in EASI score at each visit
- Change and percent change from baseline in Pruritus NRS

### 8.3. Pharmacokinetic Variables

The PK variables in the main study may include, but are not limited to, the following:

- $C_{\text{trough}}$
- $C_{\text{trough,SS}}$
- $C_{\text{last}}$
- $T_{\text{last}}$

For the sub-study,  $C_{\text{trough}}$  will be assessed.

#### 8.4. Anti-Drug Antibody Variables

Anti-drug antibody variables include status (positive or negative) and titer as follows:

- Total positive at any time
- Preexisting immunoreactivity
- Treatment-emergent
- Persistently positive
- Transiently positive
- Titer values
- Titer category
  - Low (titer <1,000)
  - Moderate ( $1,000 \leq \text{titer} \leq 10,000$ )
  - High (titer >10,000)

## 9. STATISTICAL PLAN

This section provides the basis for the statistical analysis plan (SAP) for the main study and for the sub-study. The SAP may be revised during the study (including sub-study) to accommodate amendments to the clinical study protocol and to make changes to adapt to unexpected issues in study execution and data that may affect the planned analyses. The final SAP will be issued before the database is locked.

Data collected through the implementation of new case report forms (CRFs) regarding the impact of the COVID-19 pandemic on the patients will be summarized (eg, discontinuation due to COVID-19). Any additional analyses and methods required to investigate the impact of COVID-19 on the efficacy (eg, missing data due to COVID-19) and safety will be detailed in the SAP.

Analysis variables are listed in Section 8.

### 9.1. Statistical Hypothesis

There is no statistical hypothesis in this open-label study.

### 9.2. Justification of Sample Size

No formal sample size or power calculations were performed for this study.

### 9.3. Analysis Sets

#### 9.3.1. Safety Analysis Set

The safety analysis set (SAF) includes all patients who received any study drug; it is based on the treatment received (as treated). Efficacy, treatment compliance/administration, and all clinical safety variables will be analyzed using the SAF, as treated.

#### 9.3.2. Pharmacokinetic Analysis Set

The PK population includes all treated patients who received any study drug and who had a qualified result for drug concentration at any time during the study.

#### 9.3.3. Analysis Set for Anti-Drug Antibody Data

The ADA population includes all treated patients who received any study drug and had at least 1 qualified result at any time during the study.

## 9.4. Patient Disposition

The following will be provided:

- The total number of screened patients: met the inclusion criteria regarding the target indication and signed the ICF
- The total number of patients in each analysis set
- The total number of patients who discontinued the study, and the reasons for discontinuation
- A listing of patients prematurely discontinued from treatment, along with reasons for discontinuation

## 9.5. Statistical Methods

For continuous variables, descriptive statistics will include the following: the number of patients reflected in the calculation (n), mean, median, standard deviation, minimum, and maximum.

For categorical or ordinal data, frequencies and percentages will be displayed for each category.

### 9.5.1. Demography and Baseline Characteristics

Demographic and baseline characteristics will be summarized descriptively.

### 9.5.2. Safety Analysis

Safety analysis will be based on the SAF. A summary of safety results will be presented.

#### 9.5.2.1. Adverse Events

##### Definitions

For safety variables, 2 observation periods are defined:

- The pretreatment period is defined as the time from signing the ICF to before the first dose of study drug.
- The treatment-emergent period is defined as day 1 (from start of administration of the first dose of study drug) to end of study.

Treatment-emergent adverse events are defined as those that are not present at baseline or represent the exacerbation of a preexisting condition during the treatment-emergent period.

##### Analysis

All AEs reported in this study will be coded using the currently available version of the Medical Dictionary for Regulatory Activities (MedDRA®). Coding will be to lowest level terms. The verbatim text, the preferred term (PT), and the primary system organ class (SOC) will be listed.

Summaries of all TEAEs will include:

- The number (n) and percentage (%) of patients with at least 1 TEAE by SOC and PT
- TEAEs by severity (according to the grading scale outlined in Section 7.3.1), presented by SOC and PT
- TEAEs by relationship to treatment (related, not related), presented by SOC and PT

Deaths and other SAEs will be listed and summarized.

Treatment-emergent adverse events leading to permanent treatment discontinuation will be listed and summarized.

